**PI to prospectively identify potential study participants from weekly maxillofacial and H&N surgery clinics**

- Participants to be recruited over a minimum period of 18 months; minimum of 10 patients in each treatment pathway.
- On clinic, potential participants will be asked by the PI if they are interested in taking part in the study.
- The PI, after meeting the potential participant, will confirm their eligibility.
- Eligible participants meeting inclusion and exclusion criteria will be sent an invitation letter with a participant information sheet and a consent form (emphasizing the option to either decline or accept the offer of study participation).

Do not enter study

**Consent**

- At the next routine clinical appointment, the potential patient participant's decision will be noted.
- Should the patient wish to participate, the PI will obtain their written informed consent accordingly.

**Preoperative baseline data collection (CRF01 form).**

- Medical history and screening of comorbidities (including comorbidity score & performance status), smoking and alcohol status.
- Evaluate for history of any previous radiotherapy treatment (date started and completed, regime details).
- Physical assessment (BMI, oral hygiene status).
- Detailed social history
- University of Washington QoL Questionnaire v4.
- Short-form Derriford appearance scale (DAS24).
- Liverpool oral rehabilitation questionnaire.
- 3D Photograph (Stereophotogrammetry) of the head and neck
- Baseline clinical blood tests (FBC, U&E, Clotting screen)

**Treatment allocated in normal clinical manner by surgeon to either pathway A (surgery with pre-flexed plate) or pathway B (surgery with SLM plate).**

Participant blinded to treatment allocation at this stage

**Pathway A**  
(Customized pre-flexed plate) n ≥10

**Pathway B**  
(Customized SLM plate) n ≥10

**Perioperative / inpatient data collection (CRF02 form).**

- Prior to commencing surgery, bite registration to be obtained (using viscoelastic silicone impression putty)
- At surgery, record of:
  - Times at which mandibular osteotomies are first started (cutting guides first placed onto mandible) and completed
  - Time of knife-to-skin for flap harvest
  - Time of flap detachment
  - Time of completing fixation of the plate (with flap) in its final resting position (i.e. when completion of fixation to the residual mandible)
  - Time of completing arterial anastomosis
- Record of need for any intraoperative adjustment to the plate, osteotomies and/or planned drill hole positions.
- Surgeon rating of usability, confidence of use, satisfaction with reconstructive procedure.
- Scrub nurse rating of usability, confidence of use, satisfaction with reconstructive procedure.
- Record of days-stayed on ITU / HDU and/or Ward, date of discharge.
- Record of all complications as inpatient (peri & post operative).

**6 weeks follow up** (CRF03 form).

- Physical assessment (BMI, oral hygiene status).
- University of Washington QoL questionnaire.
- Short-form Derriford appearance scale (DAS24).
- Liverpool oral rehabilitation questionnaire.
- Report on complications.
- 3D Photograph (Stereophotogrammetry) of the head and neck.
- Detailed social history (e.g. current occupation / employment)

**6 months follow up** (CRF04 form).

- Data recorded as per CRF03 form.
- Postoperative CT mandible scan (evaluation of actual vs. planned dimensions, quantitative evaluation of bony cortical union at osteotomy sites)

**1 year follow up** (CRF05 form).

- Data recorded as per CRF03 form.
- Dental assessment (including routine cone beam CT scan) and restorative dentist rating of technical and practical feasibility of prosthetic rehabilitation options

**End of study**  
Patients informed of treatment type received.

Figure 1. The JaW PrinT study design

#### **4.1 Inclusion criteria**

- Age over 18 years
- Able to provide informed consent
- A planned fibular free-flap reconstruction of the mandible
- Planned post operative surveillance CT scan 6 months following surgery

#### **4.2 Exclusion criteria**

- Clinically unfit or inappropriate (based upon prognosis/life expectancy) for reconstruction using free tissue transfer techniques
- Patients with planned surgical defects involving reconstruction of the condyle: i.e. Brown class Ic, IIc or IVc. (*Clinical use of printed plates for condylar reconstructions would in effect be 'off-licence' and non-standard treatment which is beyond the remit of an observational research study*).
- Flap failure within the study follow-up period, as this would require early removal of the flap and therefore preclude collection of follow-up outcome data. However, any flap failures (and associated clinical complications/events) will be recorded and reported.

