## 3.2 Secondary outcomes

Secondarily, the study aims to compare treatment pathways A and B for:

2. The duration of surgery (in particular individual components of the surgery such as flap warm ischaemia time, duration of osteotomies and plate fixation procedures.

3. The operators' perceptions of the overall intraoperative usability, confidence with the technique and immediate satisfaction of the surgical result.
4. The need to make minor adjustments to either the plate, osteotomy or screw holes in order to fit the plate during surgery.
5. Incidence of postoperative complications (as recorded during inpatient stay as well as at 6 weeks, 6 months and 1 year outpatient follow up visits), for example:
  - a. Localised infection
  - b. Plate extrusion/exposure
  - c. Length of hospital stay (including duration of intensive care / high-dependency / ward requirements)
  - d. Mal / non / delayed-union of the bony components of the mandibular reconstruction (from objective analysis of clinically routine postoperative CT scan imaging)
  - e. Plate fractures/failures
6. Medium-term (up to 1 year) functional outcomes, for example:
  - a. Feasibility of dental implant rehabilitation (specifically in the technical context of clinical and/or radiological perspective of bone quality and anatomy as well as in the holistic context of the patient's suitability overall, in order to determine the importance of reconstructed bony anatomy in the decision processes and planning of dental rehabilitation)
  - b. Objective evaluation of changes in dental occlusion (with the aid of dental model analysis).
  - c. Objective assessment of changes in facial aesthetics (facial symmetry based upon baseline and postoperative 3D photography (stereophotogrammetry).
7. Patient-perceived quality of life:
  - a. using a validated quality of life assessment tools:
    - i. University of Washington Quality of Life Questionnaire v4
    - ii. Short-form Derriford appearance scale (DAS24)
    - iii. Liverpool oral rehabilitation questionnaire
  - b. by time to return to work / social status at 1 year (where applicable)
8. Economic implications (with economic analysis taking the above clinical and social outcomes into account).

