### 4.5.2 Perioperative/inpatient data collection

During the inpatient phase of the participant's medical treatment, all data will be recorded on the "inpatient case report form" (CRF02).

To evaluate the presurgical dental occlusion (if occluding teeth present), a bite registration will be taken whilst the patient participant is anaesthetised. These will be obtained using a viscoelastic silicone impression material.

At surgery, overall time from knife to skin, to transferring the patient participant off the operating table will be recorded. Furthermore the timings of specific landmarks of reconstructive components of surgery will be recorded:

- Times at which mandibular osteotomies are first started (when mandibular cutting guides first touches mandible) and completed (when mandibular cutting guides removed)

- Time of knife-to-skin for flap harvest
- Time of flap detachment
- Time of completing fixation of the plate in its final resting position (i.e. when completion of fixation to the residual mandible)
- Time of completing arterial anastomosis

To evaluate the impact of cutting guides on the fit of the bony flap, the surgeon will be asked to record the number of subsequent adjustments needed to the mandibular/fibular osteotomies, drill holes and/or the plate itself.

To further evaluate the efficiency of either surgical technique (and any potential 'learning curve' effect), the surgeon and scrub nurse will be asked to provide a 5-point Likert scale rating for the following criteria at the end of the operation:

- Ease of use
- Confidence in performing the technique
- Immediate satisfaction with reconstructive component of surgery

In the immediate postoperative (inpatient) phase of recovery, dates of stay in the intensive care unit (ITU), high dependency unit (HDU) and/or the inpatient ward will be recorded, along with a final discharge date. During this period, any postoperative complications are to be recorded if/as they occur.

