#### 4.5.3 6 weeks follow up

This will include reporting of any complications since discharge from hospital, as well as repetition of some data collected in the baseline assessment, using the "6 weeks case report form" (CRF03). Specific data to be collected includes:

- Physical assessment (BMI, oral hygiene status, report on wound healing).
- University of Washington QoL questionnaire.
- Short-form Derriford appearance scale (DAS24).
- Liverpool oral rehabilitation questionnaire.
- Report on complications.
- Stereophotogrammetry (3D photography) of the head and neck.

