#### 4.5.3 6 months follow up

The "6 months case report form" (CRF04) will be used to collect identical data to that collected at 6 weeks follow-up. This follow up point is selected as in the case of cancer surgery, it is a standard follow-up point for assessment of signs of early disease recurrence. For this reason, routine medical CT scanning to evaluate for disease recurrence is performed. A 3D render of DICOM data from this clinical scan can be used to dimensionally and volumetrically compare the actual bony reconstruction with the preoperative plan, evaluating overall accuracy and precision of the reconstructive technique used. Furthermore, CT assessment of bony union will be performed using a quantitative numerical rating score, adapted from Akashi et al.(Akashi et al., 2015)

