#### 4.5.4 1 year follow up

The “1 year care report form” (CRF05) will be used to collect identical data to that collected at 6 weeks follow-up. Furthermore, in some cases routine clinical and radiographic (cone beam CT) dental assessment is performed 1 year postoperatively with a view to further dental rehabilitation (with dental implants in some patients). From this dental assessment, we would aim to evaluate the clinician’s opinion (using a 5 point Likert scale) of the patient participant’s overall suitability for dental rehabilitation (if not already in place) with a variety of possible prosthetic solutions:

- Simple dentures
- Bridge
- (Multiple) single tooth implants
- Implant retained bridge
- Implant retained dentures

Dental radiology (cone beam CT) if used as part of this routine dental assessment will also be analysed to further evaluate any bony (dimensional/volumetric/healing) changes that occur over time. Post-surgical dental occlusion would clinically routinely be evaluated with a bite registration. This can be compared to the pre-surgical bite registration to evaluate the impact of the reconstructive surgery on dental occlusion.

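### Section 4.2 excludes operated patients whose flap fails during follow-up, for a reason that covers only part of their data; section 5.0 leaves the rest to discretion

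*Protocol*

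**What the plan says.** Protocol section 4.2 (Exclusion criteria) includes "Flap failure within the study follow-up period, as this would require early removal of the flap and therefore preclude collection of follow-up outcome data". The same bullet continues: "However, any flap failures (and associated clinical complications/events) will be recorded and reported". Section 4.0 sets follow-up at 6 weeks, 6 months and 1 year, so the rule runs for a year after surgery.

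The primary outcome, dimensional accuracy (section 3.1), comes from the 6-month scan. Figure 1 describes it as "Postoperative CT mandible scan (evaluation of actual vs. planned dimensions, quantitative evaluation of bony cortical union at osteotomy sites", and the 6-month section says "A 3D render of DICOM data from this clinical scan can be used to dimensionally and volumetrically compare the actual bony reconstruction".

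Other outcomes have other sources:
- Section 4.5.2 records operative times, adjustments and operator ratings at surgery, and then "dates of stay in the intensive care unit (ITU), high dependency unit (HDU) and/or the inpatient ward will be recorded".
- The 6-week visit "This will include reporting of any complications since discharge from hospital, as well as repetition of some data collected in the baseline assessment".
- The 1-year form "will be used to collect identical data to that collected at 6 weeks follow-up".
- Section 3.2 item 5 counts "Incidence of postoperative complications (as recorded during inpatient stay as well as at 6 weeks, 6 months and 1 year outpatient follow up visits").

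Section 5.0 (Risk management) deals with exclusion that follows a clinically required departure from the protocol. Such exclusions will be disclosed, and data felt to be unaffected will be used where feasible. It does not mention flap failure.

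**The concern.** An exclusion criterion should be decidable before treatment. Consent, baseline data and the surgeon's choice of pathway all precede the operation (Figure 1, section 4.4), and flap failure follows it. The bullet therefore selects patients on a poor outcome, in a comparison that is already non-randomised.

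Reporting the failures limits the harm for one outcome only: a reader can add a reported failure back to the complication count. It does not return that patient's hospital stay, quality of life, return to work or cost to the comparison, and these are named secondary outcomes (section 3.2 items 5c, 7 and 8). If the failure comes after the 6-month CT, a valid primary measurement is also at risk of being left out.

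**Working it through.** **Step 1. Set the stated reason against the schedule.** The reason is that failure prevents collection of follow-up data.

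| Data | When and where collected | Does failure prevent collection? |
|---|---|---|
| Operative times, adjustments, operator ratings | At surgery (4.5.2) | No; complete before any postoperative failure |
| ITU, HDU and ward days; inpatient complications | As they occur (4.5.2) | No |
| Later complications, three questionnaires | 6 weeks, 6 months, 1 year | No |
| Return to work or social status, economics | Up to 1 year (3.2 items 7b and 8; Figure 1) | No |
| CT accuracy (primary), bony union | 6-month CT | Only if failure precedes the CT |
| Bone and implant feasibility | 1 year (4.5.4) | Yes, if failure precedes the assessment |
| Occlusion, facial symmetry | Bite registration; 3D photographs | Obtainable, but may describe a salvage result |

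The reason is right for the flap-dependent rows when failure comes first. It is wrong for the first four rows, and for a 6-month CT already taken.

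**Step 2. Section 4.2 beside section 5.0.** Section 4.2 excludes the patient because data cannot be collected. Section 5.0 allows unaffected data to be used after an exclusion, but it concerns clinically required deviations, depends on what is felt to be unaffected, and does not name flap failure. Read together, they leave open whether a given patient's data enter the comparison. That decision would be taken with outcome and pathway known.

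**Step 3. Illustrative size.** Inputs from the protocol: at least 10 per pathway, so at least 20 in total (4.0). The flap-failure rate *f* is not given; 3% to 10% is an assumption.

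- Chance of at least one failure at any time among 20, 1 − (1 − *f*)^20: 1 − 0.97^20 = 0.456; 1 − 0.95^20 = 0.642; 1 − 0.90^20 = 0.878.
- Chance that two arms of 10 with the same *f* have different numbers of failures, 1 − Σ Binom(k; 10, *f*)²: 0.403, 0.537 and 0.687 at 3%, 5% and 10%.
- One patient in an arm of 10: 1/10 = 10%.
- Shift in an arm mean when one of 10 is left out and differs by D from the mean *m* of the other nine: (9*m* + *m* + D)/10 − *m* = D/10. For stay, an assumed D of 5 to 20 days gives 0.5 to 2.0 days. For the overall quality-of-life item (Appendix A, 20 points per category), an assumed D of one to two categories, 20 to 40 points, gives 2 to 4 points.

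The protocol states no standard deviations, so these shifts cannot be set against the spread of the outcomes.

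**The case against.** The strongest reply is that the protocol does not hide these patients. Failures and their associated events are to be reported, the complication list in section 3.2 is introduced as examples, and section 5.0 could be read as keeping a CT or operative timings obtained before a failure. That stands in part. A reader might infer from section 4.2 alone that all such data will certainly be discarded, or that failures will be concealed. The documents support neither reading. They show only that the data may be dropped, because section 5.0 is discretionary and not tied to this event.

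Second, the exclusion is partly defensible. If failure precedes the 6-month CT, the planned measurement of the original reconstruction is lost whatever the rule says. Questionnaires, symmetry and occlusion after a failure may reflect salvage and not the plate under study. This stands, and the fix allows for it.

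Third, the size is mostly assumption. This also stands. The 46% to 88% covers failure at any time; it is not the chance of losing a usable 6-month CT, which needs failure between 6 months and 1 year, and that share is unknown. Unequal numbers between arms would still arise for CT outcomes after the fix, as unequal counts of patients not assessable. Ten per pathway is a minimum, and the protocol does not say whether it is counted before or after this exclusion, so it is not established that an arm would fall below 10.

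Fourth, this is an observational pilot without a power claim, and an analysis plan not shown may define analysis sets. The design limits the consequence. But the point is not a missing detail: the protocol states the exclusion outright, and an analysis plan that kept these patients would contradict it.

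**Conclusion.** The point holds in limited form and should be fixed. Section 4.2 uses a post-treatment outcome as an exclusion criterion, and its reason is valid only for flap-dependent assessments that fall after the failure. Because section 5.0 does not settle the matter, operated patients may be dropped from the A-versus-B comparisons or retained selectively after their outcome is known. Either can bias stay, quality of life, return to work and cost, and can lose a valid primary measurement when failure follows the 6-month CT.

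It would be tempting to say that the rule favours one pathway. The documents do not show that plate type affects flap survival, so the direction is unknown.

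The size is illustrative only. It rests on an assumed failure rate of 3% to 10%, assumed differences in stay and quality of life, and, for the 10% of an arm, the minimum of 10 being counted before exclusion.

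**What to change.** 1. Delete the flap-failure bullet from section 4.2 and bring section 5.0 into line with that change.
2. State that every operated participant stays in the analysis with all data collected, and name flap failure as a complication outcome in section 3.2 item 5.
3. Mark a flap-dependent assessment (6-month CT accuracy, bony union, 1-year bone and implant feasibility) as not assessable only when failure precedes it. Keep any 6-month CT obtained earlier. Report the not-assessable count by pathway.
4. Flag questionnaire, occlusion and symmetry data collected after a failure, and show those results with and without these patients.
5. Say whether the minimum of 10 per pathway counts all operated participants.

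The cost is essentially protocol wording; no visit or test is added to the schedule. Stay and cost data become somewhat more variable, and some post-failure data will describe a salvage result. The study questionnaires and 3D photographs already scheduled would continue for these patients. That is some extra burden if they would otherwise have stopped, since the questionnaires are not routine care and the photographs are not routine in every case (section 8.0).

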#### **4.3 Recruitment**

Participants will be recruited prospectively as they present as new patient cases to the ABMU Maxillofacial and Head & Neck cancer multidisciplinary team (MDT) clinics. Once a potential patient participant has been given his/her diagnosis and it is confirmed by the principal investigator (PI) that he/she meets the inclusion criteria, clinic staff will provide the potential participant with an invitation letter introducing the study as well as a patient information sheet and consent form (explaining the available options of participating or refraining from the study). Patients will be allowed up to 24 hours to decide whether or not to participate as to avoid any impact/delay on the scheduling of their clinical treatment. The PI will obtain written informed consent from willing participants.

#### **4.4 Treatment pathway allocation**

Upon recruitment, provision of informed consent and collection of baseline data, as per standard clinical practice, the patient participant's CT scan data is used to produce a virtual surgical plan for the mandibular resection and fibular free-flap reconstruction. Once the clinically optimal reconstructive surgical plan is established by the surgeon and technician, the choice of surgical approach will be made in the routine clinical manner by the surgeon: Pathway A (pre-flexed customized mandibular reconstruction plate and cutting guides) or to pathway B (SLM customized mandibular reconstruction plate and cutting guides). Both

treatment pathways are already part of routine/standard clinical practice at ABMUHB.

The expected/planned patient numbers for this study are based upon the historical workload of the Oral and Maxillofacial Surgery department at Abertawe Bro Morgannwg University Health Board (ABMUHB) of 10-20 cases annually. A recruitment period of 18 months with follow-up for 1 year fits within the time constraints of the postgraduate student investigator's PhD timeline.

## 4.5 Study procedures

### 4.5.1 Baseline Assessment

This will be performed using a "baseline case report form" (CRF01), which will include past medical history (with attention to any history of previous radiotherapy to the head and neck region); a 'systems review' to screen for undisclosed comorbidities as well as smoking and alcohol status. The patient participant's comorbidity and performance status scores will also be recorded. The qualitative/subjective assessment of oral hygiene status (good/fair/poor) by a consultant oral and maxillofacial surgeon will also be recorded. Collected from routine clinical preoperative tests, BMI and serum albumin concentration will be recorded as an indicator of nutritional status, along with a full blood count, urea and electrolytes and clotting screen. Baseline quality of life assessment will be performed using the University of Washington QoL Questionnaire v4 (Rogers et al., 2002)(Appendix A). A baseline assessment of the participant's perceived appearance and oral function will be evaluated using the short-form Derriford appearance scale (DAS24) (Carr et al., 2005) which is suited as a research of appearance in H&N cancers (Djan and Penington, 2013), and the Liverpool oral rehabilitation questionnaire(Pace-Balzan et al., 2006) (Appendix B) respectively. Presurgical facial aesthetics will also be evaluated by means of assessing facial symmetry with stereophotogrammetry (clinical 3D photography in the medical illustration department) of the head and neck region.

